- Chemistry panel, including Na+, K+, Cl-, HCO3-, BUN, creatinine and creatinine clearance, and total bilirubin
- Urine pregnancy test for women of childbearing potential to be done at the time of enrollment (or within one week prior to enrollment)

Laboratory work must be completed within 60 days of the enrollment date, and demonstrate the following:

- Negative urine pregnancy test
- Platelet count $> 100,000 / \mu\text{L}$
- Normal renal function with creatinine clearance $\geq 60 \text{ cc/min}$
- Total bilirubin < 3.0

All participants must demonstrate the ability to complete a daily headache questionnaire online.

Both women and men of child-bearing potential must document two methods of birth control or agree to abstinence while participating in the study. Males will need to document use of birth control to eliminate the possibility of impregnating a partner while on the medication.

Subject must agree that she/he will continue all baseline headache and non-headache medications without change for the two months duration of the study (see below). Rescue/abortive headache therapy will be allowed as needed (see below).

Once all of the above criteria have been fulfilled, the subject will continue to the baseline-monitoring phase of the clinical trial (Phase 1).

All participants will complete a Quality of Life Survey (MSQ 2.1) at the outset of the study, upon completion of study visit 3, and upon completion of the continued access phase (if applicable).

Allowed Headache Medications:

Most of the participants who will be eligible for the TRACTOR Trial will already have tried, or will be taking prophylactic migraine headache medication. During the TRACTOR Trial, to best isolate the effect of the Brilinta/ticagrelor, all participants will be asked to continue their headache medications at baseline dosage, throughout the duration of the trial. This would include any of the drugs in the following categories:

- *Beta Blockers*
- *Calcium Channel Blockers*
- *Carbonic Anhydrase Inhibitors*
- *Skeletal Muscle Relaxants*
- *Fatty Acid Derivative Anticonvulsants*
- *Anti-adrenergic agents*
- *Angiotensin Converting Enzyme Inhibitors*
- *Vitamin Supplements*

Should the need arise to change the dose, or discontinue one of the medications for any reason, a protocol deviation report will be filed. All medications for non-headache indications should be continued as well.

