All potential subjects must have migraine headache documented by a Neurologist. All potential subjects must have a documented RLS by transcranial Doppler (see details above) prior to being a candidate for inclusion into the treatment group. All potential subjects will undergo baseline blood work testing and a urine pregnancy test if indicated. All subjects will take a migraine specific Quality of Life Survey (see below) at the start of the study and at visit #3 and at the conclusion of the continued access phase of the study (if applicable). All subjects will complete a daily headache log (see below), using the REDCap Survey Tool. Each subject will monitor headaches for the first month (28 days) while on her/his baseline medication, and will monitor headaches while also taking Brilinta/ticagrelor 90 mg twice daily for the second month (28-35 days). All subjects will undergo PRU blood testing a minimum of 7 days after the start of the Brilinta/ticagrelor therapy (but prior to its completion). A subject may be eligible for two additional months of Brilinta/ticagrelor therapy, with on-going headache monitoring, if she/he has a positive response to the medication.

STUDY DRUG:

Description:

Brilinta/ticagrelor, the first of a new class of oral anti-platelet agents (cyclopentyltriazolopyrimidines), is a non-competitive, P2Y12 receptor antagonist. Following a loading dose of 180 mg, the drug will be administered in its current FDA approved (2011) dosage of 90 mg twice daily.

[figure not shown]

Figure 1

Approved Uses:

Brilinta/ticagrelor is currently FDA approved as a prescription medicine for patients who:

- Have had a recent heart attack or severe chest pain that happened because their heart wasn't getting enough oxygen
- Have had a heart attack or chest pain and are being treated with medicines or procedures to open blocked arteries in the heart

Formulation/Dosage to be Used:

Brilinta tablets for oral administration contain 90 mg of ticagrelor and the following ingredients: mannitol, dibasiccalcium phosphate, sodium starch glycolate, hydroxypropyl

cellulose, magnesium stearate, hydroxypropyl methylcellulose, titanium dioxide, talc, polyethylene glycol 400, and ferric oxide yellow.

Dose Rationale and Risk/Benefits:

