The Principal Investigator and his designees will have the primary responsibility of monitoring participant safety. All potential issues of participant safety will be reported to the Executive Committee, which will be comprised of all of the TRACTOR Migraine study Investigators. The Executive Committee will serve the function of the Data and Safety Monitoring Board for the TRACTOR Migraine Trial. This group will meet monthly, after enrollment of the first patient, and will review all safety data on an on-going basis and all SAE's within 48 hours. Enrollment, clinical outcomes and safety data will be reviewed for all patients after 20 patients have been enrolled.

DATA HANDLING AND RECORD KEEPING

Confidentiality:

Information about study subjects will be kept confidential and managed according to the requirements of the Health Insurance Portability and Accountability Act of 1996 (HIPAA). Those regulations require a signed subject authorization informing the subject of the following:

- What protected health information (PHI) will be collected from subjects in this study
- Who will have access to that information and why
- Who will use or disclose that information
- The rights of a research subject to revoke their authorization for use of their PHI.

In the event that a subject revokes authorization to collect or use PHI, the investigator, by regulation, retains the ability to use all information collected prior to the revocation of subject authorization. For subjects that have revoked authorization to collect or use PHI, attempts should be made to obtain permission to collect at least vital status (i.e. that the subject is alive) at the end of their scheduled study period.

Source Documents:

All source data, whether participant demographic information, notes from participant office visits, or participant entered headache log information will be stored in a database on a HIPAA compliant, secure server at Columbia University Medical Center. Transcranial Doppler studies will be recorded and stored in both .pdf and original format. Pharmacy records covering distribution medication will be kept at the Study Research Pharmacy. Baseline laboratory results and PRU testing results will be entered into the study database, and copies of the original documentation will be scanned into a file on the Columbia University Server.

Study Data:

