All participant/study related information will be stored in a database on secure server at Columbia University Medical Center. At the time of enrollment, the Study Coordinator will

assist the participant in entering her/his personal demographic information into the database, through a data entry page on the TRACTOR Migraine Trial Website. This webpage will also be housed on the Columbia University Server.

All daily headache log data will be entered (e-CRF's) directly by the participant via computer, smartphone, or on paper through the REDCap Survey Tool, housed on the Columbia University Server.

Record Retention:

The local study investigator will maintain all study records according to ICH-GCP and applicable regulatory requirement(s).

STUDY MONITORING, AUDITING AND INSPECTING

Monitoring Plan:

The Principal Investigator/IND Sponsor (PI) will ensure that the study protocol is followed, the data is accurate and the research subjects are safe. Safety data will be reviewed by the PI, or by his designee, as soon as it is received. Safety data will also be monitored by the Executive Committee (EC), which will review safety data and make recommendations regarding continuation, termination, or modification of the study. The EC will formally review the safety data, enrollment, and clinical outcome data after the first 20 subjects have been treated and will review all serious adverse events within 48 hours.

A dedicated Study Coordinator will review 100% of source documentation/data collected for accuracy, including all safety data. The regulatory binder, along with other essential study documents, will also be reviewed to ensure that it is complete and up to date. The first review will occur after the first subject is enrolled and will continue weekly with new enrollments. Any discrepancies will be discussed with relevant study personnel for clarification and/or correction.

The Study Coordinator will be responsible for the monitoring and day-to-day running of the trial. Her/his responsibilities will include:

- scheduling all appointments for Transcranial Doppler
- obtaining consent for participants on the day of their initial visit
- checking the data against source documentation for all participants to ensure data accuracy and integrity
- tracking blood test results for baseline evaluation and entering laboratory data into the study database
- scheduling additional study visits
- tracking participant compliance with the daily headache logs

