Appendix 1:

Trial Schedule: (see attached TRACTOR Migraine Trial Flow Sheet in Appendix 2)

Study Visit #1: At the time of the first visit, study coordinator/investigators will discuss trial and subject eligibility for participation based on migraine headache frequency. The coordinator will collect all demographic information required for the study. Participant will receive explanation of the additional testing required for trial participation. After patient has been given an opportunity to ask questions, a screening consent will be signed to perform this testing. Participant will receive a Patient Study Number. Transcranial Doppler study will be performed. If negative for right to left shunt, participant will be sent back to the referring physician for on-going clinical care. If positive for right to left shunt (Spencer Grade ≥ 2) participant will be eligible to continue in the trial. The trial will be explained in detail, including participant responsibilities, and the patient will receive written study materials. A complete TRACTOR Migraine Headache Trial consent will be signed. The participant will receive a test e-mail/text message and must demonstrate the ability to answer the headache log questions. A Quality of Life Survey will be taken. Laboratory screening is done. End of visit.

Study Phase 1:
(28 Days) Within 72 hours of the laboratory evaluation, participant will be notified of results of laboratory testing and ability to continue participation. She/he will begin to receive daily reminders (e-mail/text message) to log-in to answer the headache log questions. A follow-up appointment will be scheduled within 7 days of the completion of 28 days of headache monitoring.

Study Day 29: Headache log entries will be reviewed by the Study Coordinator to determine final eligibility for trial based on the number of headache days documented.

Study Visit #2: Must occur within seven days of completion of baseline headache log. Participant will return to receive her/his medication. She/he will receive a loading dose of 180 mg of Brilinta/ticagrelor and an additional 70 tablets and will again review the responsibilities for participation with the coordinator. The participant will be observed for 30 minutes after taking the first medication dose.

Study Phase 2:

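### The only pregnancy test in the plan comes before the 28-day baseline phase, so it is at least 28 days old at the first ticagrelor dose

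*Combined protocol and SAP*

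**What the plan says.** The baseline laboratory list under Transcranial Doppler Screening includes a "Urine pregnancy test for women of childbearing potential to be done at the time of enrollment (or within one week prior to enrollment"). The same section requires that test to be negative, adds the other laboratory limits and the contraception and medication commitments, and then states: "Once all of the above criteria have been fulfilled, the subject will continue to the baseline-monitoring phase of the clinical trial (Phase 1").

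Study Procedures mentions the test once more, again as part of baseline work: "All potential subjects will undergo baseline blood work testing and a urine pregnancy test if indicated".

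The later steps are set out in Headache Tracking and Treatment Phases and in Appendix 1:

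- Phase 1 is 28 days of headache logging without study drug.
- On Study Day 29 the coordinator settles final eligibility from the headache-day count.
- Visit 2 falls within 7 days of the completed log. It covers dispensing, the loading dose, a review of responsibilities and 30 minutes of observation.
- During Phase 2 the only laboratory test described is platelet reactivity (PRU).
- At Visit 3, responders may start about two more months of drug.

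None of these steps includes a pregnancy test.

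**The concern.** Pregnancy, and a plan to become pregnant, are listed in the Preliminary Exclusion Criteria. The expected mean age is about 30 (Potential Risks), so childbearing potential is a practical matter in this cohort. The exclusion is checked by a test placed before a month in which no drug is given, and not at the point where exposure begins.

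The other safeguards do not fill that gap. Two contraceptive methods or abstinence make conception less likely but detect nothing. Withdrawal for unanticipated pregnancy works only once the pregnancy is known. Follow-up to delivery, and reporting of congenital anomalies as serious adverse events, come after exposure. A woman who conceived during baseline without knowing it could receive the loading dose with no protocol deviation.

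This is a participant-safety point only.

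**Working it through.** The documents state no figure for the age of the test at dosing, so there is none to reproduce. The check is calendar arithmetic.

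**Inputs**

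- *a*, days from test to enrolment: 0 to 7 (baseline laboratory list).
- *n*, days to laboratory notification: 0 to 3. Appendix 1 says: "Within 72 hours of the laboratory evaluation, participant will be notified of results of laboratory testing and ability to continue participation".
- *d*, further delay before Phase 1 starts: no limit is given.
- Phase 1: 28 days.
- *v*, days from end of Phase 1 to Visit 2: 0 to 7 (Treatment Phase; Appendix 1).
- Phase 2: 28 to 35 days. Continued access: 56 to 63 days (Appendix 1).

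**Formula:** age of test at first dose = *a* + *n* + *d* + 28 + *v*

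| Case | Sum | Days |
|---|---|---|
| Minimum: test on the day Phase 1 starts, dose as soon as it ends | 0 + 0 + 0 + 28 + 0 | 28 |
| As above, Visit 2 at the end of its window | 28 + 7 | 35 |
| Test at Visit 1, 3 days for results, Visit 2 at the end of its window | 0 + 3 + 28 + 7 | 38 |
| Test a full week before enrolment, Phase 1 at once | 7 + 28 + 7 | 42 |
| As above, plus 3 days for results | 7 + 3 + 28 + 7 | 45 |
| As above, plus an assumed 7-day delay | 45 + 7 | 52 |
| As above, with an assumed 14-day delay instead | 45 + 14 | 59 |

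The 28-day minimum needs only the written order: negative test, then Phase 1, then dose. The larger values depend on where enrolment falls and how quickly Phase 1 starts, so none is a true maximum.

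**At Visit 3, before continued access:** the minimum is 28 + 28 = 56 days. With *d* = 0, the longest Phase 2 gives 38 + 35 = 73, 42 + 35 = 77 or 45 + 35 = 80 days, according to the case taken from the table.

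**At the end of continued access, with no repeat:** from 56 + 56 = 112 days to 80 + 63 = 143 days.

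**The case against.** The strongest counter-argument is that enrolment is never defined. If it meant Visit 2, the one-week window would place the test close to dosing. Some of the text leans that way. The 60-day allowance for other laboratory work has little purpose if enrolment is Visit 1, where that work is done. The Executive Committee's review is also described in two ways. Medical Monitoring has "Enrollment, clinical outcomes and safety data will be reviewed for all patients after 20 patients have been enrolled", while the Monitoring Plan has "The EC will formally review the safety data, enrollment, and clinical outcome data after the first 20 subjects have been treated".

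That reading fails on the order of events. A test first done at Visit 2 could not be a condition for entering Phase 1, as the laboratory section requires. Study Data also ties demographic entry to enrolment ("At the time of enrollment, the Study Coordinator will" help the participant enter these data), and Appendix 1 places it at Visit 1: "The coordinator will collect all demographic information required for the study". What stands is that the timing rests on an undefined word, which itself needs correcting.

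A second objection concerns the upper figures, and it is partly right. If enrolment is Visit 1 and no study test precedes it, *a* = 0 and the prompt-start maximum is 38 days. If enrolment is the start of Phase 1, notification falls inside the one-week window and the maximum is 42. The 45-day figure, and the 52 and 59 built on it, require the windows to run one after another. The 28- and 56-day minima are unaffected.

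Third, the contents of the case report forms and the consent pages were not available, so a check written there cannot be ruled out. The finding is limited to the readable text.

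Finally, few women are likely to be affected and contraception is required. Both points are true. They bear on how often the gap matters, not on whether it exists.

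**Conclusion.** The concern holds. As written, the required negative pregnancy test is at least 28 days old at the first ticagrelor dose and at least 56 days old when continued access begins, and no repeat is described. Under prompt-start assumptions the age at first dose runs up to 35 to 45 days, depending on how the windows combine. With no latest start date for Phase 1 it could be longer.

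The number of exposed pregnancies cannot be estimated. The documents give no pregnancy rate and no fetal-risk data, and at most 40 subjects of both sexes are treated, so it is probably small. The change is worth making because the exclusion is not verified when exposure starts and the correction is cheap. Confidence is medium, because enrolment is undefined and the form contents were not available.

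**What to change.** Repeat the urine pregnancy test at Visit 2 for every woman of childbearing potential, and require a negative result before the loading dose. State the window relative to first dose (for example, same day), or define enrolment, so that the timing does not hang on an undefined term. Add the test to the Visit 2 entry in Appendix 1. Optionally repeat it at Visit 3 for women entering continued access.

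Done on the day of Visit 2, the test is 0 days old at first dose instead of at least 28. The cost is one added urine test per woman of childbearing potential (fewer than 40 if any men are treated), with no extra visit. There is a small chance of delaying the dose while a positive result is confirmed.

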- Primary Efficacy Endpoint: A subject will be considered to have achieved the primary efficacy endpoint (a "Responder") if she/he has $\geq 50\%$ reduction in the number of monthly headache days during the month of therapy compared with participant's own baseline. If there is $< 50\%$ reduction in the number of migraine days, she/he will be considered a Non-Responder.
- Primary Safety Endpoint: Major bleeding episode (as defined above) or other life-threatening adverse event (see below), while taking the Brilinta/ticagrelor.

Secondary Study Endpoints:

- Secondary Efficacy Endpoints will be assessed as follows:
 - Absolute reduction in headache days as a continuous response variable.
 - Absolute reduction in headache intensity as a continuous response variable.

- Quantitative comparison of the number of monthly uses of rescue medications in the roll-in versus the treatment phase
- Comparison of time to headache resolution after rescue medications. If < 2 hours to resolution, will be considered a “successful” intervention. Will compare the percentage of successful interventions in the baseline and treatment phases.
- Secondary Safety endpoints: Non-life threatening adverse events to Brilinta/ticagrelor, including:
 - Minor bleeding
 - Allergic reactions
 - Shortness of Breath
 - Rash
 - Extreme fatigue
 - Any other symptom requiring the participant to withdraw from the study prior to completion of the one month medication administration

Subject Recruitment, Eligibility and Screening:

Study subjects will be recruited from hospital-based cardiology and headache clinic at Columbia University Medical Center, and through the private offices of the study physicians.

Preliminary Inclusion Criteria:

- Subject age 18 – 65 years
- Symptoms meet International Headache Society Criteria for Episodic Migraine or Chronic Migraine
- At least one year history of Episodic or Chronic migraine headache symptoms
- At least 6 headache days per month
- Subject agrees to use two forms of birth control or abstinence throughout duration of the study
- Subject able to complete online daily headache log
- Right to left shunt >grade 1 as determined by Transcranial Doppler evaluation

Preliminary Exclusion Criteria:

- Inability to understand the study or history of non-compliance with medical advice
- Currently taking a P2Y12 inhibitor
- Known hypersensitivity to Brilinta/ticagrelor
- History of stroke/transient ischemic attack (TIA) in the previous 6 months

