Participants who are treated with Botox injections, may be considered for the TRACTOR Migraine Trial, but should be warned of the small additional risk of bleeding at the site of the injection while on blood thinner therapy. This should be discussed with the potential participant, as part of the informed consent process. The study coordinator will be responsible for documentation of these discussions.

During the TRACTOR Trial, there will be no restrictions on abortive/rescue medications for migraine episodes, among the categories of drugs as follows:

- *Opiates*
- *Benzodiazepines*
- *Non-steroidal anti-inflammatories*
- *Aspirin*
- *Tylenol*
- *Triptans*
- *Caffeine*
- *Ergotamines*
- *Butalbital*
- *Anti-emetics*
- *Muscle Relaxants*

The use of abortive/rescue therapy will be documented in the daily headache log.

Headache Tracking and Treatment Phases:

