Baseline-Monitoring Phase (Phase 1): The subject will track her/his headaches daily for 28 days through an online survey tool (REDCap, licensed through Columbia University), to establish a baseline headache frequency. Each day, the subject will receive a text message/e-mail reminder to complete the daily headache log. The message will contain a link to log into the survey tool. During this phase, subjects will answer questions including presence or absence of headache symptoms, severity of headache symptoms, duration of symptoms, impact on daily activities, and use of rescue medication. Any headache lasting more than 24 hours will be counted as a second headache day. After 28 days of monitoring, the study coordinator will assess the subject's data to make sure the subject meets criteria for minimum headache days, and has been consistently performing the daily log. If the number of headache days is insufficient, the subject's participation will be completed. If the subject logs at least 6 headache days in the month, she/he will continue in the study. If the participant has been assigned to the Episodic arm of the study, but has >14 headache days in the screening month, or if the participant has been assigned to the Chronic arm of the study, but has <15 headache days in the screening month, she/he will NOT be reassigned, but will remain in the assigned group for analysis. The subject will then be treated with Brilinta/ticagrelor for a 28-35 day test period (Phase 2). The length of the test period will depend on the timing of the participant's follow-up visit after beginning treatment. The protocol window is 28+7 days.

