Treatment Phase (Phase 2): The subject will return for a follow-up visit to receive her/his medication within 1 week of completing the 28 day headache log. A loading dose of Brilinta/ticagrelor 180 mg will be administered in the office. Thereafter, for 28-35 days, a Brilinta/ticagrelor 90 mg tablet will be taken once in the morning and once in the evening, as close to 12 hours apart as possible. Each day, the subject will receive a text message reminder to login to the website, to record her/his headache activity. If she/he fails to login for two consecutive days, the study coordinator will place a follow-up phone call. PRU testing will be done a minimum of 7 days after the initiation of treatment, but before the medication is completed. A follow-up visit will be arranged between day 28 and day 35 days of monitoring to review efficacy, compliance, and side effects, to return unused medication, and to allow continued access to Brilinta/ticagrelor if indicated. A second Quality of Life survey will be completed.

Continued Access Phase (Phase 3): If the subject has a beneficial response to the Brilinta/ticagrelor (> 50% reduction in the average number of monthly headache days compared with the baseline), she/he will be offered continued access to the medication to complete an additional 2 months of therapy with on-going headache monitoring. A final office visit and Quality of Life Survey will be completed within 7 days of the 56th day of Phase 3 for return of unused medication, empty medication bottles and discussion about future therapeutic options. If the subject fails to have a beneficial response following the first month of treatment (Phase 2), the medication will be discontinued and participation in the study will be completed. If the subject elects to discontinue the Brilinta/ticagrelor, despite a beneficial response, participation in the study will be completed.

Outcomes Assessment/Statistical Analysis

Information from this study will be assessed to determine the feasibility of performing a larger randomized, blinded, placebo-controlled multi-center trial. We will assess not only our therapeutic drug response rate in order to estimate a required sample size for the future trial, but also our ability to recruit patients from local referring sources to estimate the time frame of such a trial. Subject compliance rate with use of daily online questionnaires will be determined. Drop-out rates, related to medication side effects will also be assessed.

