However, PLATO included only patients with acute coronary syndromes. As a result, the average patient age was 62 years. The average patient age for the TRACTOR Migraine Pilot Study cohort should be around 30 years. Historically, blood-thinning agents have a much higher propensity for causing bleeding in the older population. In addition, all patients in the PLATO trial were on dual antiplatelet therapy (with aspirin), which also increases the bleeding risk. In the TRACTOR Migraine Trial subjects will not be taking aspirin concurrently. The bleeding risks in PLATO were statistically higher, but not clinically different from that in the clopidogrel population. We had no bleeding complications in a similar migraine population, in our published clopidogrel trial.¹⁴

Other Potential Risks:

In PLATO²⁸ there were no serious clinical risks associated with the other observed side effects of the drug. Dyspnea was self-limited and mild in most. Elevation of serum uric acid and creatinine was not a clinically important issue, and in the TRACTOR Migraine Pilot will

be less important in a younger, healthier population. The bradyarrhythmic episodes noted in PLATO were also not clinically important or apparent.

Outcomes in the TRACTOR Migraine Trial will be compared to historical data from prior studies and drug manufacturing data to identify any new, unexpected adverse events or outcomes. The Executive Committee of the Trial will review all reports of adverse events.

POTENTIAL BENEFITS:

This is an observational study of the off-label use of Brilinta/ticagrelor as a primary therapy for treatment of migraine headache. In a previous study of 15 patients with severe migraine treated with clopidogrel¹⁴, >80% had improvement or complete resolution of symptoms. It is unknown if Brilinta/ticagrelor will benefit any individual subject.

ALTERNATIVES:

Subjects may choose not to participate in this study. Subjects may continue to work with their Neurologist using other preventive headache therapies such as Onabotulinumtoxin A, beta-blockers, topiramate, divalproex/sodium valproate, calcium channel blockers, and others including non-medication management.^{33,34}

WITHDRAWAL OF SUBJECTS:

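### Preventive treatment is held constant only from entry onward; with no stability period before the 28-day baseline, effects still developing from an earlier change are scored as ticagrelor response or non-response

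*Combined protocol and SAP*

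**What the plan says.** **Preventives.** Under Allowed Headache Medications, "all participants will be asked to continue their headache medications at baseline dosage, throughout the duration of the trial"; the stated purpose is to separate out the effect of ticagrelor. The requirements listed before Phase 1 add that the subject must "continue all baseline headache and non-headache medications without change for the two months duration of the study". A dose change or discontinuation during the trial leads to a protocol deviation report. The same section expects most eligible participants to have tried, or to be taking, a prophylactic.

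**Look-back.** The Preliminary Inclusion Criteria contain one look-back on migraine: "At least one year history of Episodic or Chronic migraine headache symptoms". It concerns symptoms, not treatment.

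**Botox.** "Participants who are treated with Botox injections, may be considered for the TRACTOR Migraine Trial", with a warning about bleeding at the injection site. The Alternatives section counts it among "preventive headache therapies such as Onabotulinumtoxin A, beta-blockers, topiramate" and others. No section says how long a Botox user must have been on a schedule before entry.

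**Timing.** Phase 1 lasts 28 days. The subject returns to "receive her/his medication within 1 week of completing the 28 day headache log". For Phase 2, "The protocol window is 28+7 days".

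**Endpoint and use.** A responder has at least a 50% "reduction in the number of monthly headache days during the month of therapy" relative to the subject's own baseline. Statistical Considerations calls the results descriptive, and Outcomes Assessment says the response rate will help to size the later randomized trial.

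**The concern.** Holding medication constant from entry protects the before-after comparison only if the background was already steady at entry. The plan does not require that. A patient whose preventive was started a week before Visit 1 enters at that dose, keeps it throughout and causes no deviation. If the preventive is still gaining effect when ticagrelor begins, the further fall in headache days is added to the ticagrelor effect. If a preventive was stopped shortly before Visit 1 and its benefit is still being lost, the rise is subtracted. A first Botox course given shortly before entry belongs to the same problem.

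A concurrent control arm would absorb such changes on average; this design has none. At stake is the responder rate in each cohort of 20, and through it one input to planning the next trial. That trial's own treatment comparison is protected by randomization and placebo.

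**Working it through.** The plan gives no figure on this point, so there is nothing to reproduce. The check has a reading of the text and an illustration of scale.

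**1. Text.** The eligibility criteria, the requirements before Phase 1, Allowed Headache Medications, the three phase descriptions, Study Procedures, Study Subjects and Appendices 1 and 2 contain no requirement for unchanged preventives before Day 1. The Statistical Considerations contain no exclusion or sensitivity analysis for recent changes.

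**2. Time on a fixed regimen before the first dose.** 28 days of baseline + 0 to 7 days to Visit 2 = 28 to 35 days, or 4 to 5 weeks. Only an effect still changing after that does full harm; an effect that builds up during baseline is partly in the comparator already.

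**3. Responder model.** From the documents: 28-day baseline, at least 6 baseline headache days, response at a reduction of 50% or more, 20 per cohort. Assumed: independent headache days; mean baseline of 9 days (episodic) or 18 days (chronic) per 28; a 28-day treatment count; ticagrelor effect *t*; background multiplier *m* (0.7 = recent start, 1.3 = recent stop).

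Baseline count *b* ~ Bin(28, p1), given *b* ≥ 6. Treatment count *y* ~ Bin(28, p2), with p2 = p1 × (1 − t) × m. Response if *y* ≤ *b*/2.

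| Mean baseline days | t | m = 1 | m = 0.7 | m = 1.3 |
|---|---|---|---|---|
| 9 | 0 | 6.4% | 29.6% | 0.8% |
| 9 | 0.3 | 29.6% | 60.5% | 10.7% |
| 9 | 0.5 | 58.9% | 81.8% | 36.0% |
| 18 | 0 | 0.1% | 12.6% | 0.0% |
| 18 | 0.3 | 12.6% | 56.9% | 0.7% |
| 18 | 0.5 | 54.3% | 87.4% | 20.1% |

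If half of the 30% fall is already in the baseline (baseline probability p1 × 0.85), the gain at t = 0.5 is 17.4 points (9 days) or 19.5 points (18 days), instead of 23.0 or 33.1.

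**4. Shift per cohort.** Shift = 20 × f × difference in response probability, where f is the assumed share affected and all affected subjects move the same way. The extremes in the table are both at 18 days: 0.569 − 0.126 = +0.443 (t = 0.3) and 0.201 − 0.543 = −0.342 (t = 0.5).

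- f = 0: 0
- f = 0.10: 20 × 0.10 × 0.443 = +0.89; 20 × 0.10 × (−0.342) = −0.68
- f = 0.30: 20 × 0.30 × 0.443 = +2.66; 20 × 0.30 × (−0.342) = −2.05

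Opposite movements partly cancel. The exact 95% interval for 10/20 is 27.2% to 72.8%.

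**5. Established Botox users.** Same responder rule, assuming an 84-day cycle, a 30% effect waning linearly to zero, a 3-day gap between phases and t = 0.5:

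| Timing of Phase 1 in the cycle | 9 days | 18 days |
|---|---|---|
| No Botox variation | 59% | 54% |
| Unrelated to the cycle, as the plan allows | 59% | 54% |
| Always within 14 days after an injection | about 50% | about 38% |

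Unrelated timing averages out almost completely. Forcing an early-cycle start does not.

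**The case against.** The case for leaving the plan alone is substantial. Regimens are fixed for 4 to 5 weeks before the first dose, so only slow effects matter. Patients are described as refractory, with a year of symptoms and a neurologist's documentation, and anyone whose new preventive takes them below 6 baseline headache days is released. No document figure says how many patients recently changed treatment. The larger shifts require the whole 30% change to fall after baseline. If half is already in the baseline, the largest gain over ticagrelor effects of 0 to 50% is about 25 points, or 20 × 0.10 × 0.25 = 0.5 responders at a 10% share. Results are descriptive, and an open-label rate contains placebo response anyway. The Visit 1 forms (Forms 2 to 7 in Appendix 2) are not supplied and may already capture change dates.

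All of this limits the size, and the point about the forms may make part of the remedy unnecessary. None of it supplies the missing entry condition. The width of the sampling interval will be evident from the cohort size; this error would not be, and a larger cohort would not remove it.

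A reader might go further and infer that Botox users on an established schedule are also badly unbalanced. With an assumed 84-day interval, an injection falls in exactly one phase for 28/84 + 28/84 = 67% to 28/84 + 35/84 = 75% of them. That counts injection dates, not effect. A user injected on schedule is under treatment in both phases, and step 5 shows that unrelated timing leaves the response probability almost unchanged. The figure does not measure bias.

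**Conclusion.** The gap is real: preventives need not be stable before the baseline, and in a single-arm before-after design a change still in progress is credited to, or charged against, ticagrelor. For one affected subject it can matter. With a true 50% ticagrelor effect, the chance of response moves from 59% or 54% to 82% or 87% with a further 30% fall, and to 36% or 20% with a 30% rise. For a cohort of 20 it is probably small against random error: -0.7 to +0.9 responders at a 10% share and -2.1 to +2.7 at 30%, before any cancelling.

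The share affected, the 30% change, the ticagrelor effect and the mean headache days are all assumptions. The documents therefore do not support the inference that the reported rate will be inflated: starts push it up, stops push it down, and the balance is unknown. Nor do they support calling the pilot invalid. The consequence is confined to the descriptive response rate and its use in planning. It merits correction because the correction is cheap and, unless the dates are recorded, affected subjects may not be identifiable afterwards.

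**What to change.** 1. Add an inclusion criterion: preventive drug and dose unchanged, and any Botox on an established schedule, for a fixed period before Day 1 of Phase 1. Two to three months is an example; the sponsor should set the length.
2. Record at Visit 1 the date of the last preventive change, and record all Botox injection dates before and during Phases 1 and 2, if the forms do not already do so.
3. List the responder rate descriptively with and without subjects who had a preventive start, stop or dose change in that period or during Phases 1 and 2. Show Botox users separately with their timing in the cycle.

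Do not require Phase 1 to start soon after a Botox injection. That would place every Botox user early in the cycle at baseline and late in it on treatment, turning waning into a systematic downward bias (step 5).

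The cost is one eligibility line, a few date fields and one listing. Recently changed patients wait to enter, and the listing will be imprecise at 20 per cohort. If the wait harms recruitment, items 2 and 3 alone exclude nobody and still show who may be affected.
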